This was a multicenter, double-blinded, randomized (with a randomization ratio of 1:1), controlled, parallel-group study conducted in Hong Kong. The study was carried out from July 2020 to November 2021 in two tertiary centers, which were situated in New Territories West and had an annual caseload of around 450 total joint replacements. Patients were counselled on the potential risks of general anesthesia (GA) and ESPB during the pre-anesthetic assessment, after which written informed consent would be obtained if they agreed to be recruited. This study was approved by the New Territories West Cluster Research Ethics Committee (reference number: NTWC/REC/20007), and was registered prior to patient enrollment at ClinicalTrials.gov (NCT04388553, Principal investigator: [name], Link to registration page: <https://clinicaltrials.gov/ct2/show/NCT04388553>, Date of registration: May 14, 2020). The full trial protocol can also be accessed via ClinicalTrials.gov. This manuscript was constructed in the format suggested by the Consolidated Standards of Reporting Trials (CONSORT) guideline⁷.

Eligibility criteria

To be eligible for the study, patient must be above 18 years old, under American Society of Anesthesiologists (ASA) class 1-3 and underwent primary elective unilateral THR. They should understand and accept the risks for GA and ESPB. They should also be able to use postoperative patient-controlled analgesia (PCA) and express their pain intensity in Numeric Rating Scale (NRS).

Patients with the following conditions were excluded from this study: 1) emergency case, 2) bilateral THR, 3) revision THR, 4) THR done under neuraxial technique, 5) contraindication for ESPB (i.e. patient refusal, mentally incapacitated, injection site infection, local spine pathology or surgery, coagulopathy with International Normalized Ratio > 1.4 or thrombocytopenia < 75 x 10⁹/L), 6) regular strong opioid (e.g. fentanyl, morphine, oxycodone, methadone, heroin etc.), 7) severe obstructive sleep apnea syndrome (Apnea-Hypopnea Index ≥ 30), 8) severe obesity (Body Mass Index (BMI) ≥ 35).

Randomization

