Simple randomization method was employed. Allocation concealment was achieved by drawing randomly from a set of sealed opaque envelopes with allocation inside on the day before surgery, followed by attaching it to the pre-anesthetic assessment form by the investigator. The envelope was opened by the attending anesthetist after the patient was put under GA to ensure patient blinding. If the operation was cancelled or the patient could not use PCA postoperatively, for instance, postoperative mechanical ventilation or delirium, the envelope would be put back into the pool. A CONSORT diagram illustrates the participant flow (Figure 1).

Intervention

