After the patient was put under GA (maintained with nitrous oxide and either sevoflurane or desflurane), the envelope was opened. For the treatment arm, lumbar ESPB was performed by 4 designated anesthetists. For the control arm, no injection was performed and a plaster was applied to the target skin puncture site to blind the assessor. A curved probe (Fujifilm Sonosite Edge (Washington, United States); 2-5 MHz) was placed sagittally on the flank to look for the 12th rib, which was traced medially to the transverse process of the T12. The probe was then moved one spinal level caudad to locate the L1 vertebra with the L1 transverse process in the middle of the probe. A 10 cm Pajunk Sonoplex® needle (Geisingen, Germany) was inserted in an in-plane manner to aim at the tip of the L1 transverse process. After hitting the bone, 0.5-1ml normal saline was used for hydrolocating the plane between the erector spinae muscle and the transverse process beneath it. Forty mL of 0.25% levobupivacaine (or a maximum of 2mg/kg body weight made up to the same volume) was injected into the ESP. After the block, the injection site was also covered with a plaster like the control arm. If the block was technically challenging and the anatomy was difficult to identify, the procedure would be aborted and the patient would be excluded from the study with the assignment envelope returned. After the injection, the surgeon was instructed not to infiltrate any local anesthetics into the wound. Intraoperatively, both arms received intravenous fentanyl (4 µg/kg in the first hour, 2 µg/kg in the second hour and then 1 µg/kg/hour onward) as the only analgesic and 4mg intravenous ondansetron was given. Patients from both arms were prescribed intravenous PCA fentanyl as the first-line analgesia with the following setting for at least 24 hours postoperatively: 1) bolus dose of 40% of the corrected body weight in µg fentanyl (ideal body weight in kg = body height in cm -105 (female) or -100 (male), corrected body weight = (total body weight - ideal body weight) x 0.4 + ideal body weight); 2) no background infusion; 3) lock-out time of 6 minutes; and 4) 1 hour limit of 120 - 200 µg (to be decided by the attending anesthetist). Preoperative regular oral analgesics (paracetamol 0.5 - 4 g daily, non-steroidal anti-inflammatory drugs like ibuprofen 200 - 400 mg daily or diclofenac 25 - 100 mg daily, tramadol 50 - 200 mg daily and gabapentinoids like gabapentin 100 - 900 mg daily or pregabalin 25 - 150 mg daily) were continued postoperatively unless contraindicated. Oral tramadol 50mg was prescribed as the rescue analgesic and intravenous metoclopramide 10mg was prescribed as the rescue antiemetic. Patients were instructed to request prn tramadol from ward nurse if pain control was inadequate despite intravenous fentanyl PCA.

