The data were collected by the investigator and analyzed by SPSS® 26 package. Per-protocol analysis was planned because it reflects treatment efficacy better, and any patient who deviated from the protocol (for instance, technically challenging block, postoperative mechanical ventilation and delirium) would not be analyzed. Since data of the primary outcomes, the oral morphine equivalents and the knee flexion power were not normally distributed as evidenced by skewed appearance of the histograms and p values of Shapiro-Wilk test smaller than 0.05, we used Mann-Whitney U test to compare these outcomes between treatment group and control group, while the Hodges-Lehmann estimator was employed to compute the median difference and the 95% confidence interval (CI). The proportions of postoperative nausea, postoperative vomiting and need of rescue antiemetic between two arms were compared by Chi-square test, whereas the proportions of those requiring rescue analgesia between both groups were analyzed by 2-sided Fisher's exact test (due to presence of expected count less than 5). Multivariable regression would be employed to adjust the outcomes should there be any major discrepancy (absolute standardized difference > 0.46 with n=35 in both groups as suggested by Austin¹¹) in the perioperative factors between treatment and control groups.

Sample size estimation

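### The only planned analysis is per-protocol, and one of its exclusions, the aborted block, can remove patients from the ESPB arm alone after allocation is known

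*Combined protocol and SAP*

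**What the plan says.** All the relevant text is in the Methods of the combined protocol and SAP.

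- **Statistical analysis.** One analysis set is named, with its reason: "Per-protocol analysis was planned because it reflects treatment efficacy better". The rule is that "any patient who deviated from the protocol (for instance, technically challenging block, postoperative mechanical ventilation and delirium) would not be analyzed". The reasons are given as examples, so the list is open.
- **Randomization.** "The envelope was opened by the attending anesthetist after the patient was put under GA". For a cancelled operation, or a patient who cannot use PCA afterwards, "the envelope would be put back into the pool".
- **Intervention.** If the block is difficult and the anatomy hard to identify, "the procedure would be aborted and the patient would be excluded from the study with the assignment envelope returned". On the other side, "For the control arm, no injection was performed and a plaster was applied to the target skin puncture site".
- **Safeguard (Statistical analysis).** Multivariable regression is to be used "should there be any major discrepancy (absolute standardized difference > 0.46 with n=35 in both groups" in a perioperative factor.

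No intention-to-treat, full-analysis-set or sensitivity analysis is named anywhere.

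**The concern.** Randomisation makes the arms comparable only while the patients compared are those who were allocated. Here allocation is disclosed before the block is attempted, and a patient can then be removed because of what happens during the attempt. Only patients allocated to ESPB face that test. The same anatomy in a control goes unnoticed, and no rule removes that control. The decision is also a judgement, without an objective threshold, made by staff who know the allocation.

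Returning the envelope hides the removal. Another patient can take up the vacated allocation, so a final count of 35 against 35 would not show that anyone had been lost.

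Ventilation and delirium also follow allocation. They apply to both arms under one rule, but they are post-treatment events, so removing those patients is not necessarily neutral either.

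Two things are at stake. Any difference in the primary outcomes mixes the block effect with selective removal, and no planned analysis separates them. The trial also does not estimate the effect of allocating a patient to the block, because failed attempts are left out.

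**Working it through.** **Inputs from the documents.** Sample size estimation: target difference 300 µg fentanyl, SD 438 µg; 2 NRS points, SD 2.42 (rest) and 2.48 (movement); α 0.05, power 80%, 35 per arm; pilot mean without block or infiltration 664 µg. Intervention: the PCA bolus formula. Eligibility criteria: BMI of 35 or more excluded.

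**Assumed, because the text does not give them.** f, the fraction of blocks aborted; d, how much more fentanyl those patients would use than the rest, in SDs; a reference BMI of 24; heights of 150 to 170 cm; and the same number of PCA presses at any body size.

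**1. The plan's own figure.** A two-sided two-sample t-test for 300 µg with SD 438 µg needs 34.45, rounded up to 35 per arm, with power 80.6%. The stated 35 reproduces. It contains no allowance for exclusions.

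**2. A plausible d from body size.** Bolus = 0.4 × [(total − ideal weight) × 0.4 + ideal weight]. Comparing BMI 24 with BMI 34.9:

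- Woman, 155 cm: 21.2 to 25.4 µg, +19.7%. On 664 µg that is 131 µg, and 131/438 = 0.30 SD.
- Man, 170 cm: 27.9 to 32.9 µg, +18.1%. On 664 µg that is 120 µg, and 120/438 = 0.27 SD.

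Over the assumed heights the rise is 18 to 20%, or 120 to 134 µg, so d is about 0.3 by this route. This is the only route that the documents allow one to size.

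**3. Spurious fentanyl difference.** Removing the hard-to-block fraction from one arm shifts the contrast by f × d × 438 µg:

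| f | d = 0 | d = 0.3 | d = 0.5 | d = 1 |
|---|---|---|---|---|
| 5% | 0 | 6.6 | 11.0 | 21.9 |
| 10% | 0 | 13.1 | 21.9 | 43.8 |
| 15% | 0 | 19.7 | 32.9 | 65.7 |

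As a share of 300 µg this is 2 to 7% at d = 0.3 and 7 to 22% at d = 1. Positive d favours ESPB; negative d gives the same sizes against it. For scale, the standard error of the difference is 438 × √(2/35) = 104.7 µg.

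**4. Type I error.** Simulated with the Mann-Whitney test, 35 per arm, two-sided 0.05, 20,000 replicates, normal and gamma data, over the f values above:

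- d = 0: 4.9 to 5.5%
- d = 0.3: 5.0 to 5.5%
- d = 0.5: 5.1 to 6.2%
- d = 1: 5.2 to 9.5%

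**5. Would the 0.46 trigger catch it?** Removing a fraction f whose covariate is shifted by s SD gives an expected imbalance of f × s. With f = 10% and s = 2 this is 0.20 SD, well below 0.46. For a single factor the trigger fires in about 13% of trials, against about 6% with no systematic imbalance. With f = 5% and s = 2 it fires in 8.0%.

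**6. Power when analysed as allocated.** If an aborted block gives no benefit, the effect becomes 300 × (1 − f):

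| f | Effect (µg) | Power, 35 per arm | n per arm for 80% |
|---|---|---|---|
| 0 | 300 | 80.6% | 35 |
| 5% | 285 | 76.5% | 39 |
| 10% | 270 | 72.0% | 43 |
| 15% | 255 | 67.0% | 48 |

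For pain, with effect 2 × (1 − f) over the same f, power is 92.6, 89.9, 86.6 and 82.6% (SD 2.42) and 91.4, 88.5, 84.9 and 80.7% (SD 2.48).

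**The case against.** The strongest reply is that the bias may be negligible. By the one mechanism that can be sized it is at most about 20 µg, and type I error cannot be told apart from nominal. Even that is generous: it sets every aborted patient at BMI 34.9 against a reference of 24, which the documents do not give. With a reference of 27 the same formula gives d of about 0.19 to 0.21. Equal presses is also doubtful, since patients titrate their own PCA under an hourly limit. The plan restrains f as well: spine pathology and BMI of 35 or more are excluded beforehand, four designated anaesthetists do the block, and aborting needs both technical difficulty and unclear anatomy. The flow diagram, which is not in the text available here, may show that no block was aborted.

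These points stand as limits on size. The value d = 1 is an illustration, not a bound: at f = 20% it would give 88 µg. Bias in NRS, also a primary outcome, has not been sized, and the body-size route says nothing about it. None of this supplies a missing analysis. A small aborted fraction would make the bias small, but the plan contains nothing that would show it. A flow diagram may count these patients; it does not analyse them.

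Two objections to the remedy also stand in part. Keeping only patients with outcome data still omits ventilated or delirious patients who have none. And the Statistical analysis section already reports normality results for the outcomes, so a change of primary analysis now could be post hoc.

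**Conclusion.** The concern holds. Per-protocol is the sole analysis of every primary outcome, its exclusions follow disclosure of allocation, and one of them can act only on the ESPB arm. The reason given, better reflection of efficacy, needs comparable arms, and one-sided removal undermines that comparability.

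This is a structural risk, not a demonstrated distortion. It is small under the body-size assumption, could be material if hard-to-block patients differ by around 1 SD, and is zero if they do not differ. Its direction is unknown. The planned covariate trigger would usually miss it. The sample size calculation is not in error. The point must be fixed because it affects the sole basis for the trial's conclusions and the plan offers no check on it.

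**What to change.** - Make the primary analysis as allocated: every patient whose envelope was opened and who has PCA and NRS data stays in the allocated arm, including those with an aborted block. Keep per-protocol as a labelled sensitivity analysis.
- Do not return opened envelopes to the pool.
- Report exclusions by arm and reason, and what analgesia patients with an aborted block received.
- Pre-state a sensitivity analysis for patients unable to use PCA because of ventilation or delirium. Worst-rank scoring is one option, but it makes the outcome a composite and the Hodges-Lehmann difference harder to interpret.
- The text describes a study carried out to November 2021. If recruitment has ended, apply this to the PCA and NRS records that can be recovered, state how many are missing, and label the analysis post hoc if outcomes have been seen. Envelopes already returned cannot be undone.

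**Cost.** Changes to protocol and SAP wording, and retrieval of records, some of which may be lost. Fentanyl power falls as shown above if aborted blocks give no benefit, and less if they give some or if those patients received other regional analgesia; restoring 80% would take 39, 43 or 48 per arm at 5, 10 or 15% aborted. Power for 2 NRS points stays at 80.7% or more. The clinical rule for aborting a block need not change.

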
Outcome assessment

Patients were followed up on POD1 by independent assessors from the acute pain service team consisting of a nurse and an anesthetist, who were not involved in the intraoperative care of the patient and was blinded by being instructed not to look at the anesthetic record. The primary outcomes, namely the amounts of PCA fentanyl used 12-hour and 24-hour postoperatively (in µg) and the pain intensity at rest and on movement on POD1, were assessed. NRS with a scale from 0 to 10 was adopted for pain assessment. NRS 0 means no pain while NRS 10 means the worst pain experienced⁸. The secondary outcomes were the rates of postoperative nausea (defined as feeling of having an urge to vomit)⁹ and postoperative vomiting (defined as forcing the contents of the

stomach up through the oesophagus and out of the mouth)⁹ from the end of operation till the follow-up on POD1 as recalled by the patient, the need of rescue antiemetic and analgesia in the first 24 hours postoperatively, along with knee flexion power of the operated limb in Medical Research Council (MRC) scale. The oral morphine equivalents of fentanyl and prn tramadol used at 12 hours and 24 hours postoperatively were calculated according to the opioid conversion table from the Faculty of Pain Medicine of Australian and New Zealand College of Anaesthetists (ANZCA)¹⁰. Of note, the use of antiemetic was not a surrogate of postoperative nausea or vomiting.

Statistical analysis

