A pilot study was done by retrospectively examining cases of primary unilateral THR in the two tertiary centers from January to December 2019 with postoperative PCA (infusion-plus-bolus and bolus only). The mean fentanyl use upon follow-up on the first day postoperatively (POD1) without regional block (including femoral nerve block/fascia iliaca block/lumbar plexus block/lateral cutaneous femoral nerve block/gluteal nerve block) or local anesthetics infiltration (n=36) was 664 µg, whereas that with regional block or local anesthetics infiltration (n=20) was 368 µg. To detect a reduction of fentanyl use by 300 µg which was comparable to data from the pilot study (Standard Deviation (SD) 438 µg), along with a reduction in pain score (in NRS) by 2 points (SD 2.42 for rest pain and 2.48 for movement pain) on POD1, a sample size of 35 patients was required for both treatment and control arm ($\kappa = 1$) with type 1 error (α) of 0.05 and power ($1-\beta$) of 80% in two-sample t-test assuming equal variance and normality of data distribution¹². Secondary outcomes were not taken in account of sample size calculation, and were considered to be exploratory only. No interim analysis was planned.

REFERENCES

1. Świtoń A, Wodka-Natkanięc E, Niedźwiedzki Ł, Gaździk T, Niedźwiedzki T. Activity and Quality of Life after Total Hip Arthroplasty. *Ortop Traumatol Rehabil.* 2017;19(5):441-450.

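### The Hodges-Lehmann estimate planned for MRC knee power can come out as 0 (95% CI 0 to 0) beside a significant test; a grade table with a risk difference would say more

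*Combined protocol and SAP*

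**What the plan says.** The Outcome assessment section lists "knee flexion power of the operated limb in Medical Research Council (MRC) scale" among the secondary outcomes. It is the only motor outcome in the plan.

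The Statistical analysis section groups it with the primary outcomes and the opioid equivalents: it says that "the oral morphine equivalents and the knee flexion power were not normally distributed", names Mann-Whitney U as the comparison for the whole group, and adds that "the Hodges-Lehmann estimator was employed to compute the median difference and the 95% confidence interval (CI"). No table of grades, proportion with weakness or other effect measure is planned for knee power.

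The Sample size estimation section says that "a sample size of 35 patients was required for both treatment and control arm", and that secondary outcomes are exploratory and played no part in the calculation.

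**The concern.** The Hodges-Lehmann estimate is the median of all pairwise differences between the arms, and its confidence limits are order statistics of the same differences. That works for fentanyl in micrograms. On a scale with few grades, where many patients may share the top one, most pairs can tie. The median and both limits then sit at 0 and do not move as patients in one arm become weak.

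The Introduction names limb weakness as a shortcoming of existing regional techniques, so a motor comparison matters to the case for this block. If the interval collapses, two things can go wrong:

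- A significant p appears beside 0 (0 to 0), and no planned number says how many more patients were weak.
- The p is not significant, and a zero-width interval suggests a precision that 35 per arm cannot give.

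**Working it through.** **Inputs.** From the documents: 35 per arm; 1:1 allocation ("randomized (with a randomization ratio of 1:1")); knee power on the MRC scale; Mann-Whitney with Hodges-Lehmann. Assumed, because the documents do not give them: full power is grade 5, and all weakness rates and grade mixes used below.

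**1. The plan's sample size.** "To detect a reduction of fentanyl use by 300" µg with SD 438 µg, "with type 1 error (α) of 0.05" (taken as two-sided) and power "of 80% in two-sample t-test assuming equal variance and normality of data distribution":

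n = 2 × (1.960 + 0.842)² × (438/300)² = 2 × 7.85 × 2.132 = 33.5, so 34 per arm by the normal formula. The t-based version gives 34.4, so 35. The stated 35 reproduces.

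**2. Position of the confidence limits.** There are 35 × 35 = 1,225 pairwise differences. The normal approximation for the lower rank is

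1225/2 − 1.96 × √(1225 × 71/12) = 612.5 − 166.9 = 445.6.

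The exact Mann-Whitney distribution also gives the 446th value from each end. The estimate is the 613th value.

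**3. When both limits are 0.** A difference (ESPB minus control) can be negative only if the ESPB patient is below full power. With at most 12 such patients, at most 12 × 35 = 420 differences are negative. Since 420 < 446, the lower limit cannot be below 0. The same count for controls keeps the upper limit at 0. The grades of the weak patients do not enter: with all 12 ESPB patients at grade 0 the result is still 0 (0 to 0).

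**4. What the planned test shows on the same data** (weak patients all at grade 4, the rest at grade 5).

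*12/35 against 1/35.*
- Negative differences 12 × 34 = 408; ties 23 × 34 + 12 × 1 = 794; positive 23 × 1 = 23; total 1,225.
- U = 23 + 794/2 = 420.
- Tie-corrected variance = (1225/12) × [71 − (13³ − 13 + 57³ − 57)/(70 × 69)] = 102.08 × (71 − 38.78) = 3,289; SD 57.35.
- z = (420 − 612.5)/57.35 = −3.36, p = 0.0008.
- Risk difference 11/35 = 31.4%. Wilson limits are 0.208 to 0.508 for 12/35 and 0.005 to 0.145 for 1/35.
- Newcombe lower limit: 0.314 − √[(0.343 − 0.208)² + (0.145 − 0.029)²] = 0.136. Upper limit: 0.314 + √[(0.508 − 0.343)² + (0.029 − 0.005)²] = 0.48.

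*8/35 against 1/35.*
- Negative 8 × 34 = 272; ties 27 × 34 + 8 = 926; positive 27.
- U = 27 + 463 = 490, SD 49.36, z = −2.48, p = 0.013.
- Risk difference 7/35 = 20% (Newcombe 95% CI 4 to 36).

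In both examples the planned estimate is 0 (0 to 0).

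**5. How often the two occur together.** Simulated trials with 35 per arm, weak patients split 70/30 between grades 4 and 3:

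| Assumed weakness, ESPB v control | Zero-width interval and p < 0.05 |
|---|---|
| 20% v 3% | about 66% |
| 30% v 10% | about 44% |
| 40% v 20% | about 12% |
| 50% v 20% | about 5% |

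A repeat of 4,000 trials per row gave 64%, 45%, 13% and 5%, so these figures are good to about two points.

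**The case against.** The strongest reply is that Hodges-Lehmann is not the test. A reader might infer that the plan would report no motor effect with false certainty. The documents do not support that: the stated comparison is Mann-Whitney, which flags the difference in both examples above, and nothing in the plan says that an estimate of 0 will be read as preserved power. Nor is the interval wrong for what it estimates. When most pairs tie, the median pairwise difference is 0. What stands is that this is a poor summary of an MRC grade.

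A second reply is that the collapse is conditional. The documents give no MRC distribution, and knee power in an operated limb on the first postoperative day may be reduced in many controls. That is fair, and the table shows the contradictory report becoming rare as control weakness rises. It would also be wrong to say that the interval stays at zero in general beyond 12. At 13/35 against 1/35 with every weak patient at one grade there are 13 × 34 = 442 negative differences and the interval is still 0 to 0. But with nine ESPB patients at grade 4, four at grade 3 and the control at grade 4 there are 9 × 34 + 4 × 35 = 446, and it opens to −1 to 0. It also opens at 14/35 v 1/35 and at 13/35 v 0/35. A tie-corrected rank would move that boundary outward, and which version the software uses could not be checked. The bound at 12 holds either way, because tie correction only raises the rank above 446.

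Third, the outcome is exploratory, and no primary conclusion or sample size depends on it. That stands and limits the severity.

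**Conclusion.** The point holds as a weakness in the choice of summary measure. With 35 analysed per arm, the planned estimate and interval for knee power are 0 (0 to 0) whenever no more than 12 patients in either arm are below full power, including cases where the planned test is clearly significant and the risk difference is 20% or 31%. That bound needs no assumption about the grades of the weak patients. How likely the situation is rests on weakness rates that the documents do not give, and it ranges from about 66% to about 5% of trials over the scenarios shown. This is a cheap improvement of low severity.

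**What to change.** In the Statistical analysis section, keep Mann-Whitney as the test for knee flexion power and take this outcome out of the Hodges-Lehmann list. Report instead the number of patients at each MRC grade by arm, and the proportion below grade 5 in each arm with the risk difference and a Newcombe or exact 95% CI.

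The cost is one sentence. The grades are already collected, and the analyses of the other outcomes do not change. The drawback is that a cut at grade 5 does not separate mild from severe weakness; the grade table covers that.

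### Fisher's exact test for rescue analgesia is valid but works well below its nominal 5%; Boschloo's exact test keeps the guarantee with no loss of power, and the four binary outcomes have no planned effect estimate with a confidence interval

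*Combined protocol and SAP*

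**What the plan says.** Outcome assessment lists among the secondary outcomes "the need of rescue antiemetic and analgesia in the first 24 hours postoperatively". Under Statistical analysis, nausea, vomiting and rescue antiemetic are compared by chi-square. Rescue analgesia alone is "analyzed by 2-sided Fisher's exact test (due to presence of expected count less than 5"). The same section gives the primary outcomes, the oral morphine equivalents and knee flexion power a Hodges-Lehmann median difference with a 95% CI. For the four binary outcomes it names a test and nothing else.

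The design is "randomized (with a randomization ratio of 1:1"), and the Sample size estimation section states that "a sample size of 35 patients was required for both treatment and control arm". The "type 1 error (α) of 0.05 and power" of 80% given there apply to the primary outcomes. Secondary outcomes are called exploratory and were left out of the calculation. No rescue-analgesia rates are assumed anywhere.

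**The concern.** Fisher's test conditions on the total number of events. When that total is small, few tables are possible and the attainable p-values are coarse, so the actual level falls well below 5%. The plan's reason for choosing Fisher, a small expected count, is also the setting in which it gives up most power. Other exact tests do not condition on the total and still hold 5%.

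Rescue tramadol is requested when pain control is inadequate despite the PCA, so readers need to know whether its use differed between arms when they interpret PCA fentanyl and pain scores. A non-significant result from a test running near 2% or 3%, with no interval beside it, is easily misread as no difference.

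**Working it through.** **Plan's own figure.** Inputs from Sample size estimation: difference 300 µg, SD 438 µg, two-sided alpha 0.05, power 80%. The normal approximation is n = 2(1.960 + 0.842)² × 438²/300² = 2 × 7.85 × 2.132 = 33.5, so 34 per arm. The two-sample t-test gives 35 (power 80.6%). The pain-score inputs need only 24 (rest) and 26 (movement). The stated 35 per arm is reproduced.

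**When the Fisher condition applies.** At 35 per arm the smaller expected count is half the event total. A value below 5 therefore means 9 or fewer events in all, or a common rate below 5/35 = 14.3% (or, by symmetry, above 85.7%).

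**Why the level is low.** For the most extreme split of m events, Fisher's two-sided p is 2·C(35,m)/C(70,m).
- m = 5 (0 v 5): 2 × 324,632 / 12,103,014 = 0.054
- m = 6 (0 v 6): 2 × 1,623,160 / 131,115,985 = 0.025

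Five or fewer events in total can never give p ≤ 0.05. Conditional on totals of 6, 7, 8 and 9, the level is 2.5%, 1.1%, 0.5% and 2.8%.

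**Level and power by enumeration.** For arms n₁ and n₂, the rejection probability is the sum over all tables (a, b) in the rejection region of Bin(a; n₁, p₁) × Bin(b; n₂, p₂). Setting p₁ = p₂ gives the level. Alpha 0.05 is assumed for this outcome. Boschloo orders tables by the Fisher p-value and uses the largest cut-off whose level stays at or below 5% for every common rate.

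Fisher's level at 35/35 is 0.26% at a 5% rate, 1.3% at 10% and 2.0% at 14%. Its maximum is 2.07% below 5/35 and 2.9% over all rates. Boschloo rejects when Fisher p ≤ 0.078. Its maximum level is 4.8%, and it rejects every table that Fisher rejects plus 46 more, so its power cannot be lower.

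Power at 35/35 under assumed rates, all with a smaller expected count below 5:

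| Rates | Fisher | Boschloo |
|---|---|---|
| 3% v 20% | 46% | 57% |
| 2% v 15% | 27% | 41% |
| 5% v 22% | 42% | 50% |
| 5% v 10% | 3% | 6.5% |

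The first three rows are the 8 to 14 point gain. In the last row neither test is useful.

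**Unequal arms.** Fisher's maximum level for rates below 5/35 is 3.1% at 35/34, 3.1% at 36/34 (3.0% for rates below 5/36) and 3.4% at 37/33. For the first three rate pairs, Boschloo gains about 6 to 15 points at 36/34. At 37/33 with the higher rate in the arm of 37, the gain is about 7 to 14 points. With the higher rate in the arm of 33 it almost vanishes: 62.5% v 63.2% at 3% v 20%, and 50.4% v 50.5% at 2% v 15%.

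**Borderline results at 35/35.** 0/35 v 5/35 gives Fisher p = 0.054 and Boschloo p = 0.034. 1/35 v 7/35 gives 0.055 and 0.038.

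**What an interval would show.** Take 0/35 v 5/35. The Wilson limits are 0 to 9.9% and 6.3% to 29.4%. Newcombe's interval for the difference of 14.3 points is 14.3 − √(8.0² + 9.9²) = 1.5 (from unrounded values) to 14.3 + 15.1 = 29.4 points.

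**The case against.** Fisher's test with a small expected count is standard and holds type I error at or below 5%. Choosing between conditional and unconditional exact tests is a choice between two defensible methods. This stands: the point concerns efficiency, not validity. Nor is chi-square a safe replacement, since its level reaches 5.7% at 35 per arm.

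A reader might infer that the test always runs near 2%. The documents do not support that. Simple randomization and a per-protocol set can leave arms slightly unequal, and losing one patient moves the low-rate maximum from 2.1% to 3.1%. The power gain also depends on the arm sizes and on which arm has the higher rate.

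A reader might also infer that rescue use enters no interval-based comparison. It does: Outcome assessment converts fentanyl and prn tramadol into oral morphine equivalents, and these get a Hodges-Lehmann difference with a 95% CI. That does not replace a risk difference for the proportion needing rescue, but it lowers the stakes. The glossary defines odds ratio, so some effect measure may have been intended, but the analysis section assigns none to the binary outcomes.

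Finally, the section is in the past tense and justifies Fisher by "due to presence of expected count less than 5", which suggests that counts were already known. With arms of known size, an expected count needs only the pooled total, so this does not show that results by arm had been seen. It does not rule that out either. Moving then to a test that turns 0.054 into 0.034 would be a post hoc change.

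**Conclusion.** The point holds as a modest efficiency improvement. Fisher's true level for low common rates is at most about 2.1% at 35/35 and about 3.0% to 3.4% at 35/34 to 37/33. Boschloo keeps the 5% guarantee and is never less powerful. The gain is about 8 to 14 points at 35/35 for the three larger contrasts tried, and from almost nothing to about 15 points with unequal arms.

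This rests on two independent binomial arms of about 35, alpha 0.05 carried over to this outcome, and illustrative event rates.

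It would be too strong to say that the plan is in error or that a trial conclusion is at risk. The outcome is exploratory and unpowered, and neither primary outcome depends on this test. The missing risk difference and interval for the binary outcomes is a separate gap, and it stands whichever test is kept.

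**What to change.** - If this can be settled before unblinded data are seen, name Boschloo's two-sided exact test for rescue analgesia in place of Fisher's.
- If not, keep Fisher as the stated test and report Boschloo as a labelled sensitivity analysis.
- In either case, report the risk difference with a score-based 95% CI (Newcombe or Miettinen-Nurminen, one of them named in advance) for rescue analgesia, nausea, vomiting and rescue antiemetic.

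The cost is a line or two of analysis text, with no extra patients or data. The test is less familiar and may have to be run outside SPSS. A score-based interval can exclude zero while Fisher's p is just above 0.05, as in the 0/35 v 5/35 example, so the text should say in advance that for these exploratory outcomes the estimate and interval carry the interpretation.
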